#### **8.7.1.1. Imputation of the Missing Data for the First Secondary Efficacy Analysis**

Missing ALSFRS-R total score will be imputed for the first secondary analysis. See [Section 8.6.1.1](#) for the imputation method.

Every effort will be made to collect or derive vital status at Week 24 and Week 48. In the event that missing rate of vital status is higher than expected, the missing vital status will be imputed and sensitivity analyses will be performed.

#### **8.7.2. Sensitivity Analysis of the First Secondary Efficacy Endpoint**

Sensitivity analyses for the first secondary efficacy endpoint will be conducted based on the FAS and with the common outcome variable and population-level summary. The outcome variable is the joint-rank based on the combined assessments collected up to Week 24, and the population-level summary is the stratified Mann-Whitney probability of a more favorable status in the reldesemtiv group compared to the placebo group, based on the joint ranks of the combined assessments collected up to Week 24. The sensitivity estimators and the corresponding approach for handling intercurrent events, imputation method and analytical method are shown in [Table 6](#). Likewise, sensitivity analyses will be repeated for the joint rank test with the considerations for patients with COVID-19 related deaths vs. not COVID-19 related deaths.

**Table 6: Sensitivity Estimator of the First Secondary Efficacy Endpoint**

Estimator	Approach for Intercurrent Events	Imputation Method	Analytical Method
Sensitivity Estimator 7	Observed ALSFRS-R total score collected up to Week 24 will be included in the analysis and missing data will not be imputed.	Not applicable.	Ranking and analysis methods described in Section 8.7.1 .
Sensitivity Estimator 8	For both reldesemtiv and placebo groups, missing ALSFRS-R total score due to reasons other than death will be imputed based on the distribution of the placebo group.	For each treatment group, missing ALSFRS-R total scores will be imputed using the parameters from the imputation model of the placebo distribution. The following terms will be included in the imputation model: ALSFRS-R total score from previous visits including baseline, riluzole use at baseline, and edaravone use at baseline.	Ranking and analysis methods described in Section 8.7.1 .
Sensitivity Estimator 9	
For reldesemtiv group, missing ALSFRS-R total score due to reasons other than death will be imputed successively worse (starting from 5% worse and with an increment of 5% worse for each of the next step) using tipping point approach (Ratitch 2013) until a reverse result is obtained.
 
For placebo group, missing ALSFRS-R total score due to reasons other than death will be imputed with MAR-based imputed values.
 
Missing ALSFRS-R total score due to death will be assigned a worst rank, and patients who died earlier rank worse than patients who died later.
	
For reldesemtiv group, an increment of 1 for the range of shift parameters that reverses the study result will be applied in the multiple imputation.
 
For placebo group, the imputation will be performed with the following factors included in the imputation model: ALSFRS-R total score from previous visits including baseline, riluzole use at baseline, and edaravone use at baseline.
	Ranking and analysis methods described in Section 8.7.1 .

**Table 6: Sensitivity Estimator of the First Secondary Efficacy Endpoint (Continued)**

Estimator	Approach for Intercurrent Events	Imputation Method	Analytical Method
Sensitivity Estimator 10 (COVID-19 related)	
Missing ALSFRS-R total score due to COVID-19 related deaths or reasons other than death will be imputed under a MAR paradigm.
 
Missing ALSFRS-R total score due to not COVID-19 related death will be assigned a worst rank, and patients who died earlier rank worse than patients who died later.
 
Ranking from worst to best in the following order will be applied:
 
 
• Not COVID-19 related death (worst)
 
• COVID-19 related death
 
• With dependence on assisted ventilation (either invasive or non-invasive)
 
• More decline in ALSFRS-R total score
 
• Less decline in ALSFRS-R total score (best)
 
	
The imputation will be performed for each randomized treatment group and including the following factors in the model: ALSFRS-R total score from previous visits including baseline, riluzole use at baseline, and edaravone use at baseline.
	
Ranking and analysis methods described in Section 8.7.1.

### **8.7.3. Analysis of the Remaining Secondary Efficacy Endpoints**

For the secondary endpoint of change from baseline to Week 24 in the percent predicted FVC, analysis will be based on in clinic measurements collected from the Easy One (in clinic) spirometers. Additional analyses of percent predicted FVC that include remote measurements collected from the NuvoAir spirometers will be explored (see [Section 8.8](#)).

Analyses for the remaining secondary endpoints will be performed using a MMRM with the following model terms: treatment group, baseline ALSFRS-R total score, visit, riluzole use at baseline, edaravone use at baseline as well as baseline-by-visit and treatment group-by-visit interactions. An unstructured variance-covariance matrix will be specified in the models.

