9.4.3. Secondary Endpoint(s)

The secondary endpoint(s) of the trial are:

- Combined assessment of change in ALSFRS-R total score, time to dependence on assisted ventilation (invasive or non-invasive), and survival time up to Week 24.
 - Dependence on assisted ventilation is defined as patients using non-invasive or invasive ventilation for ≥ 22 hours per day for ≥ 10 consecutive days
 - Patients with dependence on assisted ventilation are ranked lower than those with the largest drops in ALSFRS-R scores but higher than those who have died
- Change from baseline to Week 24 in the percent predicted FVC
- Change from baseline to Week 24 in the ALSAQ-40 total score
- Change from baseline to Week 24 in hand grip strength (average of both hands)

The analyses of the secondary endpoints are as follows:

The estimand of the first secondary endpoint of combined assessment of change in ALSFRS-R total score, time to dependence on assisted ventilation, and survival time up to Week 24 is the Mann-Whitney probability for more favorable status at week 24 for reldesemtiv than placebo in the paradigm where deaths have the worst ranks, patients with dependence on assisted ventilation have the next worst ranks, and the more favorable changes from baseline at week 24 in ALSFRS total score have the better ranks using a joint-rank test in the FAS (Berry 2013). The detailed ranking and imputation methods for missing data will be provided in the SAP. The joint ranks will be determined based on the combined assessments and analyzed using a stratified Wilcoxon test that compares the ranks between reldesemtiv and placebo groups while adjusting for baseline riluzole use status and baseline edaravone use status. Stratified Mann-Whitney test statistics as well as the p-value will be presented. Sensitivity analyses and associated details will be included in the SAP.

Analyses for the remaining other secondary endpoints will be performed using a MMRM with the following model terms: treatment group, baseline ALSFRS-R total score, visit, riluzole use status at baseline, edaravone use status at baseline as well as baseline-by-visit and treatment group-by-visit interactions, using an unstructured variance-covariance matrix.

To support the analysis results of the key secondary endpoints, the joint rank analyses will also be performed for change from baseline up to Week 24 in the percent predicted FVC, and for change from baseline up to Week 24 in the ALSAQ-40 total score.

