**Statistical methods:**

Unless otherwise specified, efficacy analyses will be performed on the full analysis set (FAS) by randomized treatment group. The FAS consists of all randomized patients who receive any amount of study drug and have a baseline and at least one post baseline efficacy assessment or have survival status recorded during the 24-week double-blind placebo-controlled period.

The global null hypothesis for the primary endpoint is that there is no treatment difference in the change from baseline to Week 24 in ALSFRS-R total score between patients randomized to placebo and those randomized to reldesemtiv.

The primary analysis will be conducted using a Mixed Model for Repeated Measures (MMRM) with a restricted maximum likelihood method (SAS® PROC MIXED default). The model terms will include treatment group, baseline ALSFRS-R total score, visit, baseline riluzole use, and baseline edaravone use as well as the following interaction terms: baseline ALSFRS-R total score-by-visit and treatment group-by-visit interactions. Other baseline covariates identified by stepwise selection in a regression model will also be included in the primary analysis model if they are key predictor variables for the change from baseline to Week 24 in ALSFRS-R total score based on the blinded data. The regression model used to identify baseline covariates will include pre-study disease progression rate, age and baseline percent predicted FVC as model terms. An unstructured variance-covariance matrix will be used in the primary analysis model.

Prior to applying the MMRM, missing data will be imputed using the multiple imputation procedure (Rubin 1987) for the primary analysis, and the estimates from each imputed dataset will be combined into one set of overall estimates using the SAS® PROC MIANALYZE procedure. The extent of missing data and the pattern of missing data reasons will be tabulated. Least square means (LSM), LSM difference and the corresponding standard errors, 95% confidence intervals (CI) and p-values will be presented. Multiplicity will be addressed using closed testing procedure detailed in [Section 8.5](#).

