## 5. PLANNED ANALYSES

### 5.1. Interim Analyses

Two interim analyses are planned for this trial. The interim analysis methods and the specifications of the data snapshots will be detailed in an interim analysis plan.

Twelve (12) weeks after approximately one-third or more of the planned sample size is randomized, the first interim analysis may be triggered. Its purpose is to determine if there is a lack of effect of reldesemtiv on the ALSFRS-R in CY 5031, a finding that would be inconsistent with the prior observed effect on the change from baseline at 12 weeks in ALSFRS-R total score in the Phase 2 trial, CY 5022. At this interim analysis, the Data Monitoring Committee (DMC) will receive unblinded efficacy data from the independent, third-party biostatistical group supporting them and assess the effect of reldesemtiv on the change from baseline to Week 12 in the ALSFRS-R total score. At this interim assessment, if the treatment difference for change from baseline to Week 12 in ALSFRS-R total score has a one-sided p-value larger than or equal to 0.5 (ie, the estimated treatment difference of the change from baseline at Week 12 in ALSFRS-R total score is favoring placebo), the DMC may recommend stopping the trial due to futility. This futility analysis based on the data of change from baseline to Week 12 in ALSFRS-R will not have any alpha spending. The Sponsor will monitor the blinded aggregate standard deviation of the change from baseline to Week 12 in ALSFRS-R total score periodically and possibly adjust the specified alpha before this interim analysis is conducted.

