sample size, the CDL method could allow the final analysis to include all data before and after the interim look without inflating the type-1 error. This interim analysis will spend a very small 2-sided alpha of 0.0001 for the primary endpoint as well as all individual secondary endpoints. The DMC is also expected to recommend stopping this trial due to superiority if a two-sided p-value is  $\leq$  alpha of 0.0001 for the primary endpoint as well as all individual secondary endpoints. Therefore, the significance level of 2-sided alpha of 0.0499 would be used for the final analyses for the primary endpoint and all individual secondary endpoints to control familywise error rate at overall alpha of 0.05.

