## 8.5. Multiple Comparisons and Multiplicity

The null hypothesis for the primary and secondary efficacy endpoints will be tested in a prespecified order using a closed testing procedure. This procedure will maintain the family-wise error rate at two-sided significance level of 0.0499 for all primary and secondary hypotheses tested in a confirmatory sense. The testing steps are described as follows:

- Step 1: The null hypothesis for the primary endpoint  $H_{01}$  is that there is no treatment difference in the change from baseline to Week 24 in ALSFRS-R total score between patients randomized to placebo and those randomized to reldesemtiv in the FAS. The hypothesis will be tested at the two-sided significance level of 0.0499. If this hypothesis is rejected, testing will proceed to Step 2; otherwise testing will stop.
- Step 2: The null hypotheses for the first secondary endpoint  $H_{02}$  is that the Mann-Whitney probability of a more favorable status in reldesemtiv or placebo group in the FAS is 0.5. The status is quantified by joint ranks based on the combined assessment of change in ALSFRS-R total score, time to onset of respiratory insufficiency, and survival time up to Week 24. The hypotheses will be tested at the two-sided significance level of 0.05. If this hypothesis is rejected, testing will proceed to Step 3; otherwise testing will stop.
- Step 3: The null hypotheses  $H_{03}$  is that there is no treatment difference in change from baseline to Week 24 in the percent predicted FVC between patients randomized to placebo and those randomized to reldesemtiv in the FAS. The hypotheses will be tested at the two-sided significance level of 0.05. If this hypothesis is rejected, testing will proceed to Step 4; otherwise testing will stop.
- Step 4: The null hypotheses  $H_{04}$  is that there is no treatment difference in change from baseline to Week 24 in the ALSAQ-40 total score between patients randomized to placebo and those randomized to reldesemtiv in the FAS. The hypotheses will be tested at the two-sided significance level of 0.05. If this hypothesis is rejected, testing will proceed to Step 5; otherwise testing will stop.

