### **8.8.1. Analysis of the Exploratory and Additional Efficacy Endpoint**

Exploratory analyses will be conducted based on the FAS and by the randomized treatment groups.

Proportional hazard Cox regression models will be applied for the time-to-event endpoints. For patients who had the events, the date of the first event will be used as the event date. For patients who did not have the event, data will be censored at the specified analysis time point (Week 24 or Week 48). Kaplan-Meier method will be used to summarize the time to event, and median, 95% CIs of the median, 1st and 3rd quartiles, and range will be provided.

The joint-rank test as described in [Section 8.7.1](#) will be used to analyze the endpoints of combined assessments up to the specified analysis time points, where the assessments of the endpoints will be used for ranking.

The MMRM as specified for the primary efficacy analysis (see in [Section 8.6.1](#)) except for the outcome variable, will be used for the endpoints of change from baseline to a specified time point.

A mixed linear model will be used for the endpoint of slope of change from baseline to a specified time point. The response variable will be the change from baseline to each post baseline visit up to the specified analysis time point, and the model terms will include treatment group, baseline value of the response variable, time from the first dose (a continuous variable), riluzole and edaravone use at baseline, treatment-by-baseline interaction and treatment-by-time interaction. The intercept will be set to zero.

In addition, descriptive statistics will be presented for time spent in each MiToS stage, transition of stages and progression in the degree use of both new and pre-existing DMEs (eg, from daily use progresses to dependence).

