### 1. MMRM for the primary endpoint

```
proc mixed data = artot method = reml;  
  class <usubjid> <visit> <treatment> <baseline riluzole use> <baseline edaravone use>;  
  model <change in ALSFRS-R total score> = <visit> <treatment> <baseline ALSFRS-R total score>  
    <baseline riluzole use> <baseline edaravone use> <visit>*<treatment>  
    <visit>*<baseline ALSFRS-R total score>/ddfm=kr;  
  repeated <visit> / subject = <usubjid> type = un;  
  lsmeans <visit>*<treatment> / pdiff cl;  
run;
```

Note: If the 2nd interim analysis result leads to an increase of the sample size, the final analyses will include the status of being included or excluded from the 2nd interim analysis as a covariate in the model.

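### As most naturally read, the Step 3 to 5 models for FVC, ALSAQ-40 and handgrip adjust for baseline ALSFRS-R but not for the endpoint's own baseline

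*SAP*

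**What the plan says.** SAP 8.7.3 gives one list of MMRM terms for all three endpoints: "Analyses for the remaining secondary endpoints will be performed using a MMRM with the following model terms: treatment group, baseline ALSFRS-R total score", then visit, riluzole use, edaravone use, baseline-by-visit and treatment-by-visit, with unstructured covariance. Protocol 9.4.3 has the same list: "Analyses for the remaining other secondary endpoints will be performed using a MMRM with the following model terms: treatment group, baseline ALSFRS-R total score". Baseline FVC, ALSAQ-40 and grip appear in neither.

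Three other places bear on what the baseline-by-visit term means:

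- The statistical methods summary at the front of the SAP writes the term out for the primary model: "baseline ALSFRS-R total score-by-visit and treatment group-by-visit interactions".
- The primary-endpoint code in SAP 12.5 crosses visit with baseline ALSFRS-R. Visit is categorical there ("class <usubjid> <visit> <treatment> <baseline riluzole use> <baseline edaravone use>"), so the term fits one slope per visit. No code is given for Steps 3 to 5.
- The exploratory slope model in SAP 8.8.1 does name the endpoint's own baseline: "baseline value of the response variable, time from the first dose (a continuous variable".

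The endpoints are confirmatory. Step 3 in SAP 8.5 tests the hypothesis that "there is no treatment difference in change from baseline to Week 24 in the percent predicted FVC", and Steps 4 and 5 do the same for ALSAQ-40 and grip. They are also tested at the second interim analysis: "This interim analysis will spend a very small 2-sided alpha of 0.0001 for the primary endpoint as well as all individual secondary endpoints". The methods for that look are in another document: "The interim analysis methods and the specifications of the data snapshots will be detailed in an interim analysis plan".

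**The concern.** ALSFRS-R is the only baseline score just named, the SAP summary attaches the same interaction to ALSFRS-R, and the authors name the response's own baseline where they want it. On that reading, a confirmatory test of change in FVC omits baseline FVC, while an exploratory FVC slope includes it.

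Two things are at stake. The first is precision: change is usually correlated with the starting value, and variation that own baseline would explain stays in the residual. The second is dropout. The plan expects to lose 111 of 555 patients (20%) by Week 24. SAP 6.8.1 describes imputation only for the primary and first secondary endpoints, and 8.7.3 adds none. For Steps 3 to 5 the missing-at-random assumption therefore rests on what the MMRM conditions on. Without own baseline, the model relies on dropout not depending on that baseline differently by arm.

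If own baseline was intended, the by-visit interaction alone already adjusts for it, because visit is categorical, and only the wording is at fault. Even so, two programmers could follow the same text and obtain different p-values for three confirmatory tests.

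**Working it through.** **The plan's own figure.** The sample size concerns the primary endpoint only. With a difference of 1.8, SD 5.5, 2:1 allocation, two-sided 0.05 and 90% power, the placebo arm needs about (1.960 + 1.282)² × 5.5² × 1.5 / 1.8² = 147.2, so 148. Then 148 + 296 = 444 and 444 / 0.80 = 555, with power 90.2%. The figure reproduces and is not affected. The documents give nothing comparable for FVC, ALSAQ-40 or grip, so every input below is an assumption.

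**Precision, complete data.** Scale own baseline to SD 1. Let k be the Week 24/baseline SD ratio, ρ the baseline-to-Week 24 correlation, and c the correlation of own baseline with baseline ALSFRS-R. Assume ALSFRS-R adds nothing once own baseline is known.

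- Residual variance of change with own baseline in the model: k²(1 − ρ²).
- Extra variance without it: (1 − c²)(1 − kρ)².
- SE ratio = √{[k²(1 − ρ²) + (1 − c²)(1 − kρ)²] / [k²(1 − ρ²)]}.

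Example with k = 1, ρ = 0.5, c = 0: √[(0.75 + 0.25)/0.75] = 1.155. All results for c = 0:

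| k | ρ = 0.5 | 0.7 | 0.9 | 0.95 |
|---|---|---|---|---|
| 0.8 | 1.323 | 1.262 | 1.282 | 1.387 |
| 0.9 | 1.224 | 1.154 | 1.111 | 1.125 |
| 1.0 | 1.155 | 1.085 | 1.026 | 1.013 |
| 1.1 | 1.106 | 1.042 | 1.000 | 1.009 |
| 1.2 | 1.072 | 1.017 | 1.012 | 1.068 |

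The loss vanishes where kρ is about 1. With c = 0.5, the largest value falls from 1.387 to 1.301, and 1.155 falls to 1.118.

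**Power.** Suppose an endpoint has 80% power with own baseline in the model, tested at two-sided 0.0499. Without own baseline, power is Φ[(1.961 + 0.842)/SE ratio − 1.961]:

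| Excess SE | 2.6% | 11% | 15.5% | 39% |
|---|---|---|---|---|
| Power | 78% | 71% | 68% | 52% |

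**Dropout.** Simulation under no treatment effect: 370 versus 185 patients, visits at Weeks 4, 12 and 24, unstructured covariance by maximum likelihood, c = 0.3, monotone dropout set to 20% per arm, 4,000 trials per case, test at 0.0499 (Monte Carlo SE 0.003). Dropout follows a probit model in own baseline; the slopes per SD are assumed. Bias is in baseline SDs.

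| Written model | ρ 0.5, k 1.0 | ρ 0.7, k 1.0 | ρ 0.9, k 1.0 | ρ 0.83, k 1.2 | ρ 0.8, k 0.9 |
|---|---|---|---|---|---|
| Dropout unrelated to baseline: type I | 0.047 | 0.057 | 0.055 | 0.055 | 0.050 |
| Slope 0.4, active arm only: bias | −0.045 | −0.028 | −0.008 | −0.002 | −0.025 |
| Same: type I | 0.084 | 0.065 | 0.056 | 0.047 | 0.082 |
| Slope 0.8, active arm only: bias | −0.079 | −0.045 | −0.015 | 0.000 | −0.043 |
| Same: type I | 0.127 | 0.090 | 0.062 | 0.048 | 0.116 |

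With slope 0.8 in both arms, the written model's bias is within 0.003 and its type I error 0.046 to 0.053. With own baseline added, the one-arm cases have bias within 0.002 and type I error 0.046 to 0.055. The sign of the bias depends on which patients leave which arm.

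A second simulation used a different data model: an FVC-like scale, 555 patients, about 20% loss, 3,000 trials. When dropout depended on own baseline in the active arm only and decline was related to starting level, the written model's bias was −0.33 to −0.64 points against an SE of about 1.4. With own baseline added, the bias was at most about 0.03. When decline was unrelated to starting level, both models were essentially unbiased.

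**The case against.** The best counter-case is about weight.

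- **The text is ambiguous.** Only the ambiguity is certain. The SAP 12.5 code is a prototype, to be finalised before database lock.
- **The model is valid.** It is prespecified in both documents and unbiased with complete data. The choice of covariate is largely a matter of efficiency.
- **The large figures are extreme cases.** The 39% needs a Week 24 spread smaller than baseline together with a correlation of 0.95. For FVC, entry at 65% of predicted or above narrows the baseline spread, and varied progression rates widen the later one, so k is more likely 1 or above. For k from 1.0 to 1.2 and ρ from 0.8 to 0.95, the formula gives 0% to 7%.
- **One-arm dropout is a strong assumption.** In a further run (1,500 trials, Monte Carlo SE about 0.006) with slopes of 0.8 active and 0.4 placebo, type I error was 0.045 to 0.065; with 0.4 and 0.2, 0.045 to 0.059.
- **There are mitigations.** Protocol 9.4.3 plans supportive joint-rank analyses for FVC and ALSAQ-40, the FVC slope model uses own baseline, patients who stop drug are encouraged to stay for assessments, and Steps 3 to 5 are reached only after two earlier tests succeed.

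Much of this stands as a limit on size. Nothing in the documents establishes the one-arm pattern, and the FVC argument for a small loss is reasonable. It does not remove the point. A smaller k cannot be excluded for grip or ALSAQ-40, grip has neither supportive analysis, and supportive analyses do not replace the confirmatory p-value. Gatekeeping limits when Steps 3 to 5 are reached; it does not improve their models. Either reading leaves text to correct.

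**Conclusion.** The concern holds as stated. On the natural reading, the confirmatory models for FVC, ALSAQ-40 and handgrip do not adjust for the endpoint's own baseline. This is a matter of precision and robustness to dropout. It does not invalidate the tests, and the primary endpoint and the 555 are unaffected.

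The omission is clear; its size cannot be derived from the documents. The precision loss may be near zero and is a few per cent of the SE under the inputs most favourable to the plan. It is larger if Week 24 spread is below baseline spread or the correlation is low. The bias and type I figures require dropout to depend on own baseline differently by arm and change to depend on own baseline too. They illustrate assumed inputs and are not bounds. The change should be made because it costs almost nothing and also closes the ambiguity.

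**What to change.** In SAP 8.7.3 and protocol 9.4.3, add the endpoint's own baseline and its by-visit interaction to each model, and state that baseline-by-visit means that baseline. Baseline ALSFRS-R may stay as an additional covariate. Use the same model in the interim analysis plan. Make the change before any unblinded test of these endpoints, including the second interim analysis if it is still to come; a choice made afterwards would be post hoc. Optionally do the same for the change endpoints in SAP 8.8.1 that have their own baseline and are not already adjusted for it.

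The cost is one own-baseline slope per post-baseline visit: three degrees of freedom for clinic FVC and grip (Weeks 4, 12, 24) and two for ALSAQ-40 (Weeks 12, 24). No new data are needed, since the Schedule of Activities collects all three measures at screening and Day 1. The protocol change needs IRB/IEC handling under protocol 10.1.1.
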